9.1.1. Relationship of Adverse Events to Study Drug

The relationship of AEs to study drug (Unrelated, Possible, Probable, Definite) will be summarized. Possible, probable, definite will be considered as related to study drug. If relationship to treatment is missing, it will be assumed to be related.

9.1.2. Severity of Adverse Events

All AEs will be summarized by maximum severity (1, 2, 3, 4 and 5). If a subject reports multiple occurrences of a specific event within a specific analysis period, the subject will be counted only once by the maximum severity. No imputation will be done for missing severity.

9.2. Clinical Laboratory Evaluations

Laboratory assessments, including hematology, coagulation and chemistry, will be evaluated over time on the study. All summaries will be based on the units provided by the central laboratory, no conversion will be done and missing values will not be imputed. Urinalysis assessments will only be collected at screening visit.

Summary statistics of the observed values and change from baseline will be provided at the scheduled visits for hematology, coagulation and chemistry laboratory parameters. The number and percentage of subjects with shift in normal/abnormal from baseline will be presented in a shift table at the post-baseline scheduled visits for hematology, coagulation and chemistry laboratory parameters.

Clinically significant laboratory values will be summarized for subjects meeting at least one of the criteria and change from baseline will be presented in a shift table.

- Alanine aminotransferase (ALT) $\geq 3 \times$ Upper Limit of Normal Value (ULN) and total bilirubin $\geq 2 \times$ ULN
- Aspartate aminotransferase (AST) $\geq 3 \times$ ULN and total bilirubin $\geq 2 \times$ ULN
- Albumin < 2.8 g/dL

All laboratory data will also be presented in listings.

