All prior treatments for liver cirrhosis and NASH will be recorded in the electronic case report form. All other concomitant medications taken from 30 days prior to screening and throughout the entire duration of the subject's participation in the study will be collected in the electronic case report form. Concomitant medications are defined as medications taken any time after the start of exposure to IMP. Prior medications are defined as nonstudy medications discontinued prior to the start of exposure to IMP. All other concomitant medications taken from 30 days prior to Screening and throughout the entire duration of the subject's time on study will be collected in the electronic case report form. Concomitant medications are defined as medications taken any time after the start of exposure to IMP. Prior medications are defined as medications discontinued prior to the start of exposure to IMP. The prior and concomitant medications taken during the study will be summarized using number of subjects (n) and percentage (%) by individual treatment group, for both GR-MD-02 groups combined, for the placebo group, and overall (all subjects). All prior and concomitant medications will be coded using the WHO Drug Dictionary (Version 1 Sep 2014) and further coded against Anatomic Therapeutic Chemical classification.

Laboratory and vital sign measurement will be evaluated over time using descriptive statistics. Shift analyses of relevant clinical laboratory parameters will be produced showing shifts from baseline across low, normal, and high categories presented by time point.

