## 7 Statistical and Analytical Plan

A summary of statistical methods is presented in the following sections and will be described in more detail in the statistical analysis plan (SAP).

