### **7.9.4 Safety Analyses**

All subjects receiving any part of at least 1 infusion of study treatment will be evaluated for safety. The safety analyses will include evaluation of the incidence of treatment-emergent adverse events (TEAEs), grade 3 or greater AEs, SAEs and AEs leading to discontinuation of study treatment using the Common Terminology Criteria for Adverse Events Version 4.0 or higher. Laboratory and vital sign measurement will be evaluated over time on study using descriptive statistics. Shift analyses of relevant clinical laboratory parameters will be produced showing shifts across low, normal, and high categories.

All heart rate (beats per minute), 12-lead ECG parameters, PR interval (milliseconds), QRS interval (milliseconds), QT interval (milliseconds), and QTc interval (milliseconds) will be measured, and overall interpretation will be summarized for all subjects by study visit including the last visit of the study.

Electrocardiogram parameters will be summarized using descriptive statistics. Mean and mean change from baseline values will be presented for every scheduled assessment. Change from baseline will be calculated as the postbaseline measurement minus the baseline measurement. If either the baseline or postbaseline value is missing, the observation will not be included in the change from baseline summary. In addition, counts and percentages for ECG overall interpretation (normal, abnormal, clinically significant, and not clinically significant) will be presented for each scheduled assessment.

For physical examinations, the results (normal, abnormal, or not done) by body system of the full physical examination at the randomization visit and follow-up visits will be summarized with descriptive statistics by treatment group and visit. For physical examinations performed at postrandomization time points, the number and percentage of subjects with no change or any significant changes since the previous examination will be presented by treatment received. In addition, a shift table will be included to summarize the number and percentage of subjects with changes from baseline to each postrandomization visit by body system for each treatment group. The number and percentage of subjects with normal and abnormal results (clinically significant versus not clinically significant) for each body system will be presented by treatment group.

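### SAP 9.2 tabulates laboratory shifts as normal/abnormal where the supplied protocol plans low/normal/high, so that table cannot show the direction of a shift

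*SAP*

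**What the plan says.** The protocol describes the laboratory shift analysis twice. Its synopsis, under Statistical Methods, says: "Shift analyses of relevant clinical laboratory parameters will be produced showing shifts from baseline across low, normal, and high categories presented by time point". Section 7.9.4 repeats the three categories: "Shift analyses of relevant clinical laboratory parameters will be produced showing shifts across low, normal, and high categories". Neither place says which parameters count as relevant.

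SAP 9.2 covers hematology, coagulation and chemistry. At post-baseline scheduled visits, subjects "with shift in normal/abnormal from baseline will be presented in a shift table". The SAP does not divide abnormal into low and high, and it gives no reason for using two categories.

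The same SAP section plans three other laboratory outputs:

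- For the same panels, "Summary statistics of the observed values and change from baseline will be provided at the scheduled visits".
- "Clinically significant laboratory values will be summarized for subjects meeting at least one of the criteria". The criteria are ALT at least 3 × ULN with total bilirubin at least 2 × ULN, AST at least 3 × ULN with total bilirubin at least 2 × ULN, and albumin below 2.8 g/dL. These also get a shift table.
- "All laboratory data will also be presented in listings".

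**The concern.** Laboratory abnormalities are a named safety endpoint in both documents (protocol 7.4, SAP 3.2.4). A shift table shows, arm by arm, how many subjects crossed a reference limit and in which direction. Many of the planned tests can be abnormal on either side with different meanings: white cells and platelets in protocol 6.4.8, and sodium, potassium, glucose, calcium and magnesium in protocol 6.4.9.

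If low and high are pooled, an arm that drifts down and an arm that drifts up can produce the same table. The SAP is meant to add detail to the protocol's statistical methods, but on this item it gives less.

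**Working it through.** The documents state no figure to reproduce. The check compares the texts and counts table cells.

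**Categories.** Protocol synopsis: low, normal, high, from baseline, by time point. Protocol 7.9.4: low, normal, high. SAP 9.2: normal, abnormal, from baseline, at post-baseline scheduled visits. The documents agree on the baseline reference and on tabulating by visit. They differ in the number of categories.

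**Cells per parameter and visit.** Protocol: 3 × 3 = 9. SAP: 2 × 2 = 4. The nine map onto the four as follows.

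| SAP cell | Protocol cells merged | Count |
|---|---|---|
| normal to normal | normal to normal | 1 |
| normal to abnormal | normal to low; normal to high | 2 |
| abnormal to normal | low to normal; high to normal | 2 |
| abnormal to abnormal | low to low; high to high; low to high; high to low | 4 |

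The counts add up: 1 + 2 + 2 + 4 = 9. Only the first cell keeps its meaning. In the last, two stable states are pooled with two reversals, so a reversal reads as no shift.

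**Between-arm comparison.** Suppose *k* subjects in one arm move from normal to low, and *k* of the same number in another arm move from normal to high. Both arms show *k* under normal to abnormal, and the table reports no difference.

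**Whether other planned outputs replace the lost information.**

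- Change-from-baseline summaries are signed but describe the group. If equal numbers of subjects rise and fall by the same amount, the mean change is zero. Quartiles and extremes (SAP section 4) would show the spread, but not how many subjects crossed which limit.
- The threshold table is directional, but only for ALT or AST combined with total bilirubin, and for low albumin. It has no criterion for platelets, hemoglobin, white cells, creatinine, electrolytes, glucose or coagulation.
- Listings hold each subject's direction but do not compare arms.
- The SAP Addendum of 26 January 2018 adds repeated-measures models for a few laboratory variables, platelet count among them. These are post hoc comparisons of mean change, and the Addendum does not touch the shift tables.

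**Whether normal/abnormal is shorthand.** Protocol 7.9.4 uses low/normal/high for laboratory values and, within the same section, normal and abnormal for ECG interpretation and physical examination. SAP 9.5 and 9.6 also use normal and abnormal for examination and ECG, where no low or high exists. The two vocabularies are kept apart in the protocol, so a programmer working from SAP 9.2 alone would reasonably build a two-category table.

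**The case against.** The strongest reply is that this is a wording mismatch in one descriptive table. Direction remains visible elsewhere, as the working shows. In addition, protocol 6.4.7 has clinically significant abnormal results recorded as adverse events, unless they belong to the underlying disease and are no more severe than expected. No efficacy test depends on the table, and neither document ties a DSMB decision rule to it. A count of cells also measures no effect on patients. All of this stands and keeps the point minor. It does not supply the missing directional comparison between arms for the two-sided parameters.

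A second reply is that the protocol supplied is the original of 20 February 2015 and the SAP evidently follows different text in places. The SAP restricts entry to Ishak stage 5 or 6, uses another PK sampling scheme, adds two histology staging endpoints, and codes adverse events with a later MedDRA version. An amendment not supplied may have changed the shift categories too. That cannot be ruled out, so the finding is a mismatch between the supplied documents, not proof that the SAP departs from the protocol version that governed it.

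A third reply is that normal/abnormal may be shorthand, since no table shells are supplied. That is possible, but nothing in the SAP says so.

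A reader might also infer that the abnormal-to-abnormal cell will be large because many subjects with cirrhosis start with abnormal values. The documents give no baseline abnormality rate. The exclusion limits in protocol 4.1.2 do admit abnormal values (platelets down to 60 000/mm³, transaminases up to 10 × ULN), but they also restrict the population to Child-Turcotte-Pugh Class A. The size of that cell is unknown, and the point does not rest on it.

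**Conclusion.** The mismatch holds as a minor point. Taken literally, SAP 9.2 merges nine shift categories into four for each parameter and visit, pools opposite shifts, and shows reversals as no change. For platelets, white cells, sodium, potassium, glucose and similar tests, no other planned output gives a directional categorical comparison between arms.

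Two stronger readings are tempting and not supported. One is that the direction of laboratory change is lost from the safety report; it is lost only from the general shift table. The other is that protocol 7.9.4 requires low/normal/high tables for every test in all three panels. It speaks only of relevant parameters and leaves them undefined, and the SAP's coverage by panel is explicit where the protocol's is not.

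The conclusion assumes that SAP 9.2 means what it says and that no later amendment altered the categories. Sample size, power, type I error and every efficacy result are unaffected.

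**What to change.** In SAP 9.2, replace normal/abnormal with low, normal and high against the laboratory reference range, and tabulate baseline category by category at each scheduled post-baseline visit, by treatment group, for hematology, coagulation and chemistry. This matches the categories in the protocol synopsis and section 7.9.4 and keeps the SAP's own coverage of panels. If a later protocol amendment introduced the two-category form, cite it in SAP 9.2. If the change was deliberate for another reason, state the reason.

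No new data are needed. SAP 9.2 mentions the central laboratory only as the source of units and does not say who supplies the ranges. However, classifying a two-sided test as abnormal already requires both limits, so they must be available. The cost is reprogramming the shift tables. Because the Addendum refers to a final SAP, record the change with a date; if the tables have already been run, add the three-category version beside them.

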#### **6.4.5.2 Eliciting and Documenting Adverse Events**

All AEs (serious and nonserious) will be assessed beginning at screening and up to 42 days after the last dose of IMP.

Serious AEs that occur more than 42 days after the last dose of IMP need not be reported unless the investigator considers them related to IMP.

At every study visit, subjects will be asked a standard nonleading question to elicit any medically related changes in their well-being. They will also be asked if they have been hospitalized, had any accidents, used any new medications, or changed concomitant medication regimens (both prescription and over-the-counter medications).

In addition to subject observations, AEs identified from any study data (eg, laboratory values, physical examination findings, ECG changes) or identified from review of other documents that are relevant to subject safety will be documented on the AE page in the eCRF.

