3.2.5. PK Endpoint

The PK endpoints include plasma concentrations and population PK parameters of GR-MD-02.

The population PK analysis will be described in a separate modeling analysis plan.

4. General Statistical Considerations

Study day for events on or after the date of the first infusion will be defined as the number of days from the date of the first infusion of IMP, plus 1 day, so that the date of the first

infusion will be defined as Day 1. For events before the date of the first infusion, study day will be calculated as the difference in days between the date of the first infusion and the date of interest. Thus, the day before the date of the first infusion will be defined as Day -1. This means there will be no study day zero (0).

Baseline is defined as the last assessment prior to the first infusion of IMP. All baseline measurements must have been collected prior to administration of first infusion of IMP. Measurements that are obtained after the first infusion of IMP will be considered as post-baseline values. If the measurement of a variable is not made on a given subject prior to the first infusion of IMP, then that subject will be considered not to have a baseline value for that variable. Change from baseline is defined as post-baseline assessment minus baseline assessment.

Continuous data will be described using the following descriptive statistics: the number of subjects (n), mean, standard deviation (SD), median, the first quartile (Q1), the third quartile (Q3), minimum and maximum, where appropriate. Categorical data will be summarized using the frequency count (n) and percentage (%) of subjects for each category, where appropriate.

Unless otherwise specified, all statistical tests and confident intervals (CIs) will be two-sided and conducted at the 0.05 significance level. If analysis variables are not normally distributed, Poisson-regression model (or the negative binomial) will be applied for counts data.

No imputation will be applied for missing data unless otherwise specified.

All collected data used for safety and efficacy evaluations will be presented in listings. Data will be displayed in all listings sorted by treatment group and subject identifier unless specified otherwise.

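### SAP 9.2 sets a size threshold for ALT or AST only jointly with total bilirubin of at least 2×ULN, so no planned laboratory table counts large isolated enzyme rises

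*SAP*

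**What the plan says.** SAP 9.2 plans four kinds of laboratory output.

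- **By-visit descriptives.** "Summary statistics of the observed values and change from baseline will be provided at the scheduled visits". SAP section 4 defines the statistics for continuous data as "the number of subjects (n), mean, standard deviation (SD), median, the first quartile (Q1), the third quartile (Q3), minimum and maximum".
- **Shift table.** This gives the number and percentage of subjects with "shift in normal/abnormal from baseline will be presented in a shift table at the post-baseline scheduled visits". Protocol 7.9.4 uses three categories instead: "Shift analyses of relevant clinical laboratory parameters will be produced showing shifts across low, normal, and high categories".
- **Clinically significant values.** "Clinically significant laboratory values will be summarized for subjects meeting at least one of the criteria". The criteria are ALT ≥3×ULN with total bilirubin ≥2×ULN; AST ≥3×ULN with total bilirubin ≥2×ULN; and albumin <2.8 g/dL. The bilirubin condition stands inside each enzyme bullet (the ALT one reads, in part, "Upper Limit of Normal Value (ULN) and total bilirubin"), so it cannot be read as a separate alternative.
- **Listings.** "All laboratory data will also be presented in listings".

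The SAP addendum adds ALT and the AST/ALT ratio as repeated-measures models of mean change. Laboratory abnormalities are a named safety endpoint (protocol 7.4, SAP 3.2.4).

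**The concern.** To compare arms for liver safety, a reader needs the number of subjects per arm whose ALT or AST rose a long way. The combined criterion is a sound, specific signal and should stay, but it is the only place where a laboratory table attaches a size to an enzyme value, and it ignores any enzyme rise without raised bilirubin. If the other tables do not separate large rises from small ones, the count has to be extracted by hand from listings or read from adverse event tables that depend on what investigators chose to report. The visit summaries and the shift table are also tied to scheduled visits, so a peak found at an unscheduled draw is missing from both.

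**Working it through.** The plan gives no figure to reproduce on this point. The check applies the stated rules to example subjects. All values below are constructed and illustrative; none come from the documents. Enzymes and bilirubin are in multiples of ULN.

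**Step 1: the criteria as a rule.** A subject is summarised if (ALT ≥3 and bilirubin ≥2) or (AST ≥3 and bilirubin ≥2) or albumin <2.8 g/dL. With albumin 4 g/dL:

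| ALT | AST | Bilirubin | Summarised? |
|---|---|---|---|
| 3 | 1 | 1 | no |
| 5 | 5 | 1 | no |
| 10 | 8 | 1 | no |
| 20 | 20 | 1.9 | no |
| 3 | 1 | 2 | yes |
| 1 | 3 | 2 | yes |

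Without the bilirubin condition (or low albumin), no enzyme value is large enough to qualify.

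**Step 2: the shift table.** Bilirubin is 1.5 in the first row and 1.0 in the rest; albumin is not low. Every row meets 0 of the 3 criteria. The last column shows where each subject would fall under the rows proposed below.

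| Enzyme, baseline to peak | Shift cell now | Proposed rows |
|---|---|---|
| 4 to 11 | abnormal to abnormal | ≥10×ULN, new; ≥2× baseline (11/4 = 2.75) |
| 4 to 4.2 | abnormal to abnormal | ≥3×ULN, not new; 4.2/4 = 1.05, no baseline band |
| 6 to 6.1 | abnormal to abnormal | ≥5×ULN, not new; 6.1/6 = 1.02, no baseline band |
| 1.1 to 2.2 | abnormal to abnormal | ≥2× baseline only (2.2/1.1 = 2.0) |
| 0.9 to 15 | normal to abnormal | ≥10×ULN, new |
| 0.9 to 1.1 | normal to abnormal | none |

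From a normal baseline the rise is counted but its size is lost. From an abnormal baseline there is no shift at all. The protocol's low/normal/high version behaves the same way (high to high, normal to high).

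**Step 3: the by-visit statistics.** Take an arm of 52 and the change from baseline at one visit. In every version the lowest 40 changes are evenly spaced from −1 to 0.5 (sum −10, sum of squares 10.38). The top 12 are:

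- 2 risers of ≥5: 0.5 five times, 0.67, 1.84, 2.98, 3, 3, 7, 7
- 3 risers: 0.62, 0.79, 0.82, 0.82, 1.01, 1.15, 1.20, 1.31, 1.32, 5.81, 6.13, 7
- 4 risers: 0.62, 0.66, 0.70, 0.71, 0.72, 0.73, 0.83, 0.85, 5.00, 5.00, 5.16, 7

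To rounding, each top-12 set has sum 28 and sum of squares 130. So each time:

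- mean = (−10 + 28)/52 = 0.346
- SD = √[(10.38 + 130 − 52 × 0.346²)/51] = 1.62
- Q1 (mean of 13th and 14th values) = −0.519; median (26th and 27th) = −0.019; Q3 (39th and 40th) = 0.481
- minimum −1, maximum 7, n = 52

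All eight statistics agree to two decimals, while the number of risers runs from 2/52 = 3.8% to 4/52 = 7.7%.

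**Step 4: adverse event tables.** Events identified from laboratory values go on the adverse event page (protocol 6.4.5.2). They are graded by CTCAE 4.03 and tabulated as Grade 3 or greater and by maximum severity (SAP 9.1 and 9.1.2). This does give counts by arm, but only for values the investigator judged clinically significant. Protocol 6.4.7 also leaves out results attributed to the underlying disease unless the investigator thinks them worse than the subject's condition would predict. In a NASH population, transaminases are an obvious candidate for that exemption.

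**The case against.** The case against is mainly about weight. Nothing in the documents requires enzyme-only bands, no statement is contradicted and no data are lost. Chemistry is drawn at five scheduled post-baseline visits, the visit maximum shows that a large rise occurred, and with about 52 subjects per arm the listings identify who had it. The most extreme rises are those an investigator is most likely to report as more severe than expected. Some would also lead to withdrawal (protocol 4.2.1) and appear among events leading to discontinuation. The data safety monitoring board reviews safety at three set times, with outputs not visible here. The SAP also appears to follow a later protocol than the one posted (for example, Ishak stages 5 and 6 only), so section 6.4.7 and the 10×ULN entry limit may have changed.

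Much of this stands as context and keeps the point small. A maximum flags one subject but does not count them, and a listing does not compare arms. The adverse event and discontinuation routes pass through individual judgement, and a board's interim output does not replace a final table. The 10×ULN limit is not needed: size is lost from a normal baseline, and the shift disappears for any entry value above ULN. The exemption in 6.4.7 may have been amended, but reporting as an adverse event would still depend on the investigator.

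It is also fair that Step 3 covers change at one visit, whereas observed values are summarised too and at every visit. If all baselines were equal, observed values would differ from changes by a constant and would match as well, but this remains a demonstration that the count cannot be recovered, not a forecast.

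**Conclusion.** The concern holds. Under the stated rules, no planned laboratory table gives the number of subjects per arm with a large ALT or AST rise unless bilirubin is also at least 2×ULN. The shift table counts a rise from a normal baseline without its size and shows no shift for a rise from an abnormal one. The descriptives do not determine the count: 2, 3 or 4 subjects in 52 fit the same eight values in the constructed example. Adverse event tables cover the gap only partly.

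The conclusion on the laboratory tables rests on the SAP text alone; how far adverse event tables fill the gap rests partly on protocol 6.4.7 as posted. The effect on this trial's safety conclusions cannot be sized from the documents. It is an improvement worth considering, at low cost, and it does not touch the efficacy analysis or the type I error rate.

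**What to change.** Keep the three existing criteria. Add to SAP 9.2, by treatment group in the safety set, counts and percentages of subjects by maximum post-baseline ALT and AST, regardless of bilirubin and including unscheduled values:

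1. For all subjects, multiples of ULN (for example ≥3×, ≥5×, ≥10×), each with the number not already in that band at baseline.
2. In addition, for subjects above ULN at baseline, multiples of baseline (for example ≥2×, ≥3×, ≥5×).

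Using both scales lets a rise such as 4 to 11×ULN show on each, while a stable high value is not read as a rise. A rise from a normal baseline that stays below 3×ULN (0.9 to 2.9, say) remains only a normal-to-abnormal shift, even though 2.9/0.9 = 3.22. The counts should be read against placebo. The cut-offs are examples for display, not rules for managing subjects.

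The cost is SAP wording and a few table rows from data already collected, with no new samples or visits. The drawback is slightly longer safety output, and the lowest bands will pick up some natural fluctuation in every arm.
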